## Statistical Analysis Plan

### 11.5. VITAL SIGNS

Body temperature will be summarized in °C. If body temperature is recorded as °F, then temperature will be converted to °C using:

Temperature (in °C) = 5/9 (Temperature [in °F]-32).

Summary tables by visit and time point and change from baseline to visit and time point for each vital sign parameter will be provided.

### 11.6. ECG

Summary tables by visit and time point and change from baseline to visit and time point for each ECG parameter (pulse rate (bpm), R-R (msec), QRS interval (msec), QT interval (msec), QTcB interval (msec) and QTcF interval (msec)) will be provided.

The number and percentage of patients will be reported who have QTcB or QTcF values: >450 ms; > 480 ms; and > 500 ms. The number and percentage of patients will be reported who have changes from baseline in QTcB or QTcF: > 30 ms; and > 60 ms.

Additionally, the number and percentage of patients will be reported for patients who have the following QTcB or QTcF values and changes in QTcB or QTcF from baseline: QTcF > 450 ms and change in QTcF > 30 ms; QTcF > 450 ms and change in QTcF > 60 ms; QTcF > 480 ms and change in QTcF > 30 ms; QTcF > 480 ms and change in QTcF > 60 ms; QTcF > 500 ms and change in QTcF > 30 ms; QTcF > 500 ms and change in QTcF > 60 ms.

The maximum on-treatment change in QTcF from baseline versus the Cmax will be displayed graphically for both AZD9150 and AZD5069, using unique symbols for each of the following 4 QTcF categories: < 450 ms; >= 450 ms to <480 ms; >=480 ms to < 500 ms; and > 500 ms.

All ECG results including overall results of the ECGs recorded as 'normal', 'abnormal, not clinically significant (NCS)' or 'abnormal, clinically significant (CS)' will be listed by treatment group at each time point.

### 11.7. PHYSICAL EXAMINATION

Physical examination data will be listed.

## Statistical Analysis Plan

### 11.8. ECOG PERFORMANCE STATUS

For Part A and Part B, the ECOG performance status at baseline will be summarized using the number and percentage of patients within each ECOG performance category by treatment group. All ECOG data will be listed.

### 11.9. IMMUNOGENICITY

In all patients treated with MEDI4736, venous blood samples for IM assessments will be obtained. Using results from the tiered analysis, the number and percentage of patients who are positive for ADA will be summarized by visit and treatment group using the Safety Set. For patients who test positive for ADA, titer values will be listed. Samples will be stored for assessing the neutralization capacity in the future.

In all patients treated with AZD9150, the number and percentage of patients who are positive for anti-AZD9150 antibody will be summarized by visit and treatment group using the Safety set. For patients who test positive for anti-AZD9150 antibody, titer values will be listed.

For AZD9150 treated patients, the geometric mean AZD9150 concentration versus time profiles will be presented by anti-AZD9150 antibody status (i.e., positive or negative). PK parameters ( $C_{max}$  and AUC) of AZD9150 will be presented separately for anti-AZD9150 antibody positive and negative patients. A patient will be considered to be antibody positive if at least one post-treatment antibody assessment was positive.

Similarly, for MEDI4736 treated patients, the geometric mean trough concentration versus time profile will be presented by ADA status.  $C_{max}$  values of MEDI4736 treated patients will be presented separately for ADA-positive and ADA-negative patients.

The association between immune-related AEs and ADA positivity will be assessed by comparing the odds of a patient having an immune-related AE in the ADA positive group to the odds of a patient having an immune-related AE in the ADA negative group. Separate odds ratios (adjusted by replacing zero cells with 0.5) will be calculated for AZD9150 and MEDI4736 ADAs.

For Part B, a logistic regression model may be used to estimate the probability of having an objective response using treatment group and anti-PD-(L)1 status as factors and the maximum post-treatment antibody titer level as a continuous variable.

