5.7 Immunogenicity

In all patients treated with MEDI4736, venous blood samples for IM assessments will be obtained. This applies to all patients in the dose-escalation Part A and patients randomised to receive MEDI4736 in the dose-expansion Part B (i.e., treatment arms B1, B2, B3, B4, B7, and B8). The date and time of collection of each sample will be recorded.

Blood samples for IM (5 mL) will be collected predose on Day 1 of Cycle 1, on Day 15 of Cycle 2, and on Day 1 of each subsequent even-numbered cycle. For patients who discontinue MEDI4736, a blood sample will also be collected during follow-up at 90 days after the last dose of MEDI4736.

Blood samples for IM determination of a potential anti-AZD9150 antibody (2 mL) will be collected predose from all patients treated with AZD9150 on Day -7 (B8 only), Day 1 of Cycle 1, Day 1 of Cycle 2, and Day 1 of each subsequent even-numbered cycle.

Samples will be measured for the presence of ADA using a validated bridging immunoassay. Tiered analysis will be performed to include screening, confirmatory, and titre assay components and positive-negative cut points will be employed that were statistically determined from drug naïve validation samples.

Samples will be stored for assessing the neutralisation capacity in the future.

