**Table 2. Definition of Analysis Populations**

| Analysis Set    | Definition  |
|------------------------|--|
| All Patients           | All patients who provided written informed consent (i.e., including screen failures)   |
| Full Analysis          | All patients who were either assigned or randomized to study.  |
| Safety                 | All patients who received at least 1 dose of AZD9150, AZD5069, or MEDI4736.  |
| Pharmacokinetics (PK)  | All dosed patients with reportable AZD9150, AZD5069, treme or MEDI4736 plasma concentrations except for important protocol deviation. The important protocol deviations will be determined by the clinical team during the Blind Data Review Meeting (BRDM) planned to take place just prior to the final Database Lock (DBL). |
| Pharmacodynamics (PDN) | All patients who provided biological samples for pharmacodynamic research except for important protocol deviation. The important protocol deviations will be determined by the clinical team during the Blind Data Review Meeting (BRDM) planned to take place just prior to the final Database Lock (DBL).                    |

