## Statistical Analysis Plan

### 6. GENERAL ASPECTS FOR STATISTICAL ANALYSIS

#### 6.1. GENERAL METHODS

Statistical analyses of the demographic, safety, and efficacy data will be performed by [REDACTED] under the direction of the Early Clinical Biometrics Group, AstraZeneca.

[REDACTED] will perform all PK and PD analyses. [REDACTED] will provide data listings of the administration information for the collection of PK and PD samples. [REDACTED] will provide summaries of descriptive statistics for the PK and PD parameters derived by [REDACTED].

AstraZeneca will be responsible for creating the playbook used to communicate CRM model recommendations to the SRC in dose-escalation Part A. However, [REDACTED] will independently generate a copy of the playbook that can serve as a back-up, if needed. AstraZeneca will also be responsible for providing all summaries of predictive probability calculations to be performed in Part B.

The methods outlined below apply to both Part A and Part B unless otherwise specified.

- SAS version 9.3 or higher will be for all statistical analyses, excluding analyses that are Bayesian or involve the CRM.
- R version 3.1.2 or higher software and modules (e.g.: dferm package) will be used for CRM analyses in Part A and for the Bayesian analyses in Part B.
- All patients who provided informed consent will be accounted for in this study and have data from patients who were randomized or dosed included in the patient data listings.
- Listings will be sorted by treatment group (see Section 6.1.1 for ordering), patient number and, if applicable, by assessment date and time unless otherwise noted. Patients who are screen failures will be presented in a separate listing.
- The total number of patients in the treatment group and dose level (N) will be used as the denominator for percentage calculations, unless stated otherwise in the table shell.
- Continuous variables, including pharmacodynamic variables, will be summarized using the number of observations (n), mean, standard deviation (StD), median,

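### By-visit antibody percentages default to the full treatment-group N, not the patients tested at that visit, so they are understated once samples are missing, unless a table shell overrides the default

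*SAP*

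**What the plan says.** For antibodies to MEDI4736, SAP Section 11.9 plans that "the number and percentage of patients who are positive for ADA will be summarized by visit and treatment group using the Safety Set". For AZD9150 it plans that patients "positive for anti-AZD9150 antibody will be summarized by visit and treatment group using the Safety set". Neither sentence says what the count is divided by.

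The divisor comes from SAP Section 6.1: "The total number of patients in the treatment group and dose level (N) will be used as the denominator for percentage calculations, unless stated otherwise". That sentence goes on to name the table shell as the place where an exception would appear. SAP Section 15 puts the shells in a separate document.

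The Safety Set in SAP Table 2 is "All patients who received at least 1 dose of AZD9150, AZD5069, or MEDI4736". It does not require an antibody sample, and Table 2 defines no antibody-evaluable set.

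Protocol Section 5.7 schedules the MEDI4736 antibody samples before dosing on Day 1 of Cycle 1, then "on Day 15 of Cycle 2, and on Day 1 of each subsequent even-numbered cycle". It adds one sample off treatment: "For patients who discontinue MEDI4736, a blood sample will also be collected during follow-up at 90 days after the last dose of MEDI4736". For anti-AZD9150 antibody, the same section lists Day 1 of Cycles 1 and 2 and of later even-numbered cycles, plus Day -7 in Arm B8. A 90-day sample after AZD9150 appears only in the Arm B8 footnote to Protocol Table 8. Protocol Section 4.2.3 ends immunogenicity follow-up early if the patient starts another anticancer therapy.

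**The concern.** A patient who gives no sample at a visit cannot be counted as positive there. If that patient stays in the divisor, the table in effect treats the missing sample as a negative result. Under the Section 6.1 default this happens at every visit after the patient stops scheduled sampling, and at any visit where a sample is missed.

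Two readings of the table then go wrong. Read down the visits, a rate that is steady among tested patients looks as if it were declining. Read across arms, the arm whose patients stay on treatment longer looks more immunogenic because more of them are still sampled. The error can only run towards under-reporting.

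Immunogenicity of both drugs is a secondary objective (Protocol Section 2.2, SAP Section 3.2), and SAP Section 4.6 lists antibodies as a secondary safety endpoint. SAP Section 2 expects the planned analyses to go into regulatory submissions or publications. The by-visit table is the plan's main summary of how often antibodies occur.

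**Working it through.** The documents state no antibody rate, no number of antibody samples and no retention rate, so there is no planned figure to reproduce. The check is the arithmetic of the ratio, followed by illustrations with assumed values.

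**Definitions at one visit.** N is the number of Safety Set patients in the treatment group and dose level (the SAP 6.1 default). n is the number with an antibody result at that visit. k is the number positive, which can only come from the n tested.

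**Formula.** Printed rate = k/N = (k/n) × (n/N), that is, positivity among those tested × share tested. The relative understatement is 1 − n/N, whatever the true positivity.

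**Illustration 1: whole patients.** N = 48 is the approximate size planned for each of Arms B7 and B8 (SAP 3.6.2). The numbers tested and positive are assumed, with one patient in six positive throughout.

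| Tested n | Positive k | k/n | Printed k/N |
|---|---|---|---|
| 48 | 8 | 16.7% | 16.7% |
| 36 | 6 | 16.7% | 12.5% |
| 24 | 4 | 16.7% | 8.3% |
| 12 | 2 | 16.7% | 4.2% |

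Positivity among tested patients does not change, yet the printed column falls to a quarter of its starting value (12/48 = 0.25).

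**Illustration 2: an assumed positivity of 20%.** With 70%, 50%, 30% or 15% of the group tested:
- 0.20 × 0.70 = 14%
- 0.20 × 0.50 = 10%
- 0.20 × 0.30 = 6%
- 0.20 × 0.15 = 3%

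**Illustration 3: two arms at the same visit.** Both have 20% positivity among those tested. If 75% are tested in one and 50% in the other, the table prints 0.20 × 0.75 = 15% and 0.20 × 0.50 = 10%. The difference comes only from time on treatment.

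**Illustration 4: rising positivity.** If positivity among those tested doubles from 10% with everyone tested to 20% with half tested, the table prints 0.10 × 1.00 = 10% and then 0.20 × 0.50 = 10%. The printed rate is flat. It has not fallen, but the second value is half the rate among tested patients.

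**Is loss of samples plausible?** Cycles last 28 days, so Day 1 of Cycle 4 falls 3 × 28 = 84 days after Day 1 of Cycle 1, and Day 1 of Cycle 6 falls 5 × 28 = 140 days after. Protocol Section 1.1.5 cites a projected median survival of about 3.5 months in patients progressing on platinum regimens. That is background for one population and not a retention rate for this trial. It does make some loss of samples by the later visits likely in the second-line arms.

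**The case against.** The strongest objection is that the divisor is not settled. Section 11.9 names a population, and the Section 6.1 rule gives way to the table shells, which cannot be seen. This stands as a limit on certainty: a shell may already use the number tested. It does not remove the point, because the only rule in the SAP text gives the full N, and Section 11.9 makes no exception to it.

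Second, SAP Section 6.1 also has categorical summaries show a number of observations. If each visit row prints it, a reader could recover the rate among tested patients. That would help, but it leaves the printed percentage unchanged.

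Third, SAP Section 6.3 rules out imputation unless specified, and where the SAP wants missing data counted as failure it says so, as in Section 8.3.9 for unknown vital status at 12 months. This suggests that no negative imputation was intended. It still does not set a denominator, and dividing by N has the same effect as imputing.

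Three stronger readings are tempting and should not be adopted:
- A reader might infer that the printed rate must fall over time. It need not: if positivity among those tested rises quickly enough, the printed rate stays level or rises, while remaining understated.
- A reader might infer that patients lost in the lead-in, before any MEDI4736, are certainly in the divisor because the Safety Set admits them. For anti-AZD9150 the summary sentence in Section 11.9 is limited to patients who received AZD9150. For MEDI4736 a similar restriction opens the paragraph, though it is attached to the sampling sentence, so the matter is doubtful.
- A reader might infer that the antibody association analyses are affected. The analyses by antibody status of pharmacokinetics, immune-related adverse events (Section 11.9) and response (Section 8.3.11) classify patients as positive or negative overall and do not use the by-visit percentage.

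**Conclusion.** The concern holds in a limited form. Read as written, SAP Sections 11.9 and 6.1 together divide the by-visit counts for both antibodies by the full group N, and the printed percentage is then the rate among tested patients scaled down by the share tested. The relative understatement equals the untested share: with half the group tested, an assumed 20% prints as 10%.

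This rests on two conditions: that the table shells do not override the Section 6.1 default, and that some patients have no result at the visit. The positivity and retention values above are assumptions, and the documents set no threshold for acceptable bias.

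The reach is narrow. The endpoint is descriptive, SAP Section 11 plans no inferential testing of safety data, and objective response, predictive-power monitoring and sample size do not depend on it. The change is still worth making because it corrects a stated rule that gives a misleading percentage.

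**What to change.** In SAP Section 11.9, for MEDI4736 antibodies and anti-AZD9150 antibody alike, state that the denominator at each visit is the patients treated with the relevant drug who have an evaluable antibody result at that visit. Print that n beside the count and percentage, and bring the table shells into line. Naming exposure to the relevant drug also settles the doubt about patients lost during the lead-in.

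Optionally, add a patient-level rate: the proportion ever positive after baseline among treated patients with at least one post-baseline result. This is an addition, not a correction.

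The cost is one SAP sentence and one column in the antibody tables. No new data are needed, and neither the sampling schedule nor the protocol has to change.

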## Statistical Analysis Plan

### **11.10. EXPLORATORY ANALYSES**

#### **11.10.1. Blood-borne Biomarkers**

These results will be reported separately and will not be part of the CSR.

#### **11.10.2. Tumour-based Biomarkers**

These results will be reported separately and will not be part of the CSR.

#### **11.10.3. Sensitivity Analysis for Overall Survival**

In dose-expansion Part B, some patients may switch from a monotherapy arm to the corresponding combination drug. In such cases, the patient's time for OS will be censored at the time of the switch to the combination drug. Consequently, the follow-up time for the monotherapy and combination drugs may differ.

A sensitivity analysis may be performed to compare the follow-up times of the monotherapy and combination drug arms B5 and B6 in Part B. An overall measure of follow-up will be calculated for OS by calculating the median time from randomization to death or censoring for all patients, regardless of treatment arm using the Kaplan-Meier methodology. Then, this same calculation will be repeated for each arm but including all observed deaths and censoring patients at last contact agnostic to the time of switch.

## Statistical Analysis Plan

### 12. INTERIM ANALYSES

There will be no interim analysis for dose-escalation Part A.

The dose-expansion Part B will use an adaptive approach to sample size based on Bayesian statistical methodology, so the number of actively enrolling treatment arms may decrease as the study continues. For the 2 combination arms in the anti-PD-(L)1 naïve patients (B3 and B4), once 12 efficacy outcomes are observed in the first 12 efficacy evaluable patients in each arm, a predictive probability calculation will be used to assess the chance of observing at least 8 of 35 responses (either PR or CR) in each arm. The method of calculating predictive probability will be based on a parameter free approach to predictive probability as it applies to variables that follow a binomial distribution (Jennison and Turnbull 2000). Predictive probability (chance to observe at least 8 of 35 responses) will be recalculated following the observation of the efficacy outcome in each efficacy evaluable patient as they were dosed in the trial. Following the observation of any patient's outcome, if predictive probability falls below 20%, the corresponding arm will be stopped. If predictive probability remains at or above 20% following the 19th efficacy evaluable patient, then an interim analysis will be conducted following the 20th efficacy evaluable patient. Each of the combination arms will continue to enrol patients up to a maximum of 35 efficacy evaluable patients following the interim analysis if at least 5 of 20 patients have responded with at least a PR.

For the 2 combination arms in the anti-PD-(L)1 treated patients (B1 and B2), the predictive probability to assess the chance of observing at least 3 of 20 of responses (either PR or CR) will be calculated when observing the efficacy outcomes for the first 10 efficacy evaluable patients, then recalculated following the observation of efficacy outcome in each efficacy patients. However, no formal interim analysis will be conducted for the 2 combination arms in the anti-PD-(L)1 treated patients.

Recruitment will continue while predictive power is measured. If an arm is to be stopped, no new patients will be recruited but patients who are already on study will continue in accordance with study guidelines outlined in Section 4 of the protocol.

If at least 2 CRs or PRs are observed in the first 20 patients in either of the 2 pretreated expansion arms, an additional 25 to 32 patients may be enrolled to that particular pretreated combination arm.

#### 12.1.1. Efficacy Endpoints for Interim Analysis

Interim analysis of efficacy will be limited to the following variables:

## Statistical Analysis Plan

- ORR
- Predictive probability for observing at least 8 of 35 overall responses (CR or PR)
- DOR

No confidence limits will be produced for the ORR. The calculation of predictive probability will be performed by AstraZeneca.

DOR will be summarized as described in Section 8.3.3 of this SAP.

### **12.1.2. Safety Endpoints for Interim Analysis**

Interim analyses of the safety endpoints will use the same methods, summaries and listings identified in Sections 11.2 through 11.7 of this SAP.

## Statistical Analysis Plan

### **13. CHANGE FROM ANALYSIS PLANNED IN PROTOCOL**

For PK, PD, and Efficacy Analysis Sets defined to analyze data for this study, we modified the definitions slightly by adding the phrase “except for important protocol deviation”. The important protocol deviations will be determined by the clinical team during the BRDM planned to take place just prior to the final DBL.

## **15. MOCK-UPS**

### **15.1. TABLE MOCK-UPS**

Figure mock-ups will be provided in a separate document.

### **15.2. FIGURE MOCK-UPS**

Figure mock-ups will be provided in a separate document.

### **15.3. LISTING MOCK-UPS**

Listing mock-up will be provided in a separate document.

## Statistical Analysis Plan

### **16. APPENDICES**

Appendix 1 - Playbook Summarizing Dose-escalation Recommendations from the CRM
